7.1.2 Secondary Aims

Means and standard deviations will be estimated for count outcomes. We will report the two-sided p-value for statistical significance of the difference in means of count outcomes.

The frequencies of atrial fibrillation and stroke or other focal neurologic event will be modeled with Poisson regression with the length of follow-up time as the offset. Potential risk factors included in this model will be selected based on univariate test results, as well as clinical significance. Logistic regression will be used to model the incidence of all-cause and stroke-related mortality after cardiac surgery, respectively.

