1.2 Background Literature

Atrial fibrillation (AF) is the most common cardiac arrhythmia and frequently presents in association with mitral, other valvular and coronary artery disease, notably in the presence of poorer left ventricular function (1,2). Preoperative AF is reported commonly in patients undergoing cardiac surgery, with an incidence of 10-20% (2-8). Even if treated, preoperative AF is associated with a higher incidence of in-hospital postoperative AF, stroke, other cardiac morbidity and mortality (2,6,9-11).

Conventional management of postoperative AF assumes that it results from self-limited causes, such as postoperative pericarditis, surgical stress, and sympathetic stimulation in patients underlying heart disease that can be treated with short-term antiarrhythmics, heart rate reduction, anti-coagulants and anti-platelet agents. However, it is well-known that AF in the immediate postoperative period is associated with increased risk of post-discharge AF and stroke. Observed incidences range widely (3-25%) depending principally on the duration of follow-up and the mode of monitoring (12-14). These studies did not use continuous ECG monitoring to detect AF recurrence, and therefore may have underestimated the incidence of AF by missing asymptomatic AF. Using continuous ECG monitoring the incidence of at least one electrocardiographic episode of AF lasting longer than six minutes is much higher; 60% over the entire follow-up period and 39% occurring more than 3-months after surgery (15).

Thromboembolic stroke is a major preventable cause of morbidity and mortality in patients with post-operative AF (16-18). Studies have demonstrated a risk-unadjusted two to ten-fold increase in embolic events and a threefold increased risk of cardiac death in patients with postoperative AF (12,19,20).

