2 STUDY SUMMARY AND AIMS

The purpose of this study is to determine the incidence, risk factors and adverse events consequent upon atrial fibrillation after cardiac surgery, as well as the association between prior atrial fibrillation and postoperative atrial fibrillation. The study uses information from local Cardiac Surgical Programs to describe the preoperative medical state and immediate post-operative state. Additionally, information from the post-discharge period will be provided by CHIA, by matching the two sources of information using HIPAA-waived data such as medical record number, date of birth, gender and last name. Once matched, the data are stripped of identifiers.

2.1 Study Design:

We will employ a retrospective cohort design, examining patients who underwent cardiac surgery at Cardiac Surgical Programs in Massachusetts between 1/1/2012 and 12/31/2016, with a follow-up period that extends to 12/31/2017. The study examines the risk factors and incidence of post-operative atrial fibrillation, stroke and other focal neurological events after discharge from hospital.

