4 ESTIMATION OF ACCESSIBLE EFFECT SIZE

This will be a retrospective cohort study. Patients will be included in the study based on the inclusion and exclusion criteria. All statistical tests will be two-sided and the statistical significance level will be set at 0.05 unless otherwise stated. Assuming 50,000 patients will be included in the analysis, among which 4000 (8%) have prior AF, we will have 80% power to detect a Cohen's effect size of 0.046 at the 0.05 significance level. If 25% of the patients who do not have prior AF have postoperative AF, a Cohen's effect size of 0.046 is corresponding to a 2% difference in the incidence of postoperative AF.

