7.1.1 Primary Aims

The standard Cox proportional hazards model will be used to model time to first atrial fibrillation occurrence and time to first stroke or other focal neurologic event, after discharge from hospital,

respectively. The potential risk factors included will be selected based on their univariate association with first event status, as well as clinical significance. Hazard ratios with 95% confidence intervals will be reported with a two-sided p-value for statistical significance. The proportional hazard assumption will be evaluated using graphical tool, and by including time dependent covariate terms.

Since there might be repeated occurrences of atrial fibrillation and stroke or other focal neurologic event for each patient, we will use the Andersen-Gill (AG) model and the Prentice, Williams and Peterson (PWP) models to analyze recurrent events data. The AG model is suitable when the interest is in the overall effect on the intensity of the occurrence of a recurrent event. The PWP models allow us to evaluate the effects of risk factors for the kth event after discharge from hospital, as well as the effects of risk factors for the kth event since the time from the previous event (47). Hazard ratios with 95% confidence intervals will be reported with a two-sided p-value for statistical significance. For time-to-event data analyses, death will be considered a censoring event.

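### The planned p-value for the difference in mean event counts ignores time observed, so it can mislead when mean follow-up differs between the compared groups

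*Combined protocol and SAP*

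**What the plan says.** Section 7.1.2 (Secondary Aims) opens with count outcomes: "Means and standard deviations will be estimated for count outcomes". It then commits to a test: "We will report the two-sided p-value for statistical significance of the difference in means of count outcomes". It names no groups, no test statistic and no person-time denominator. Section 4 fixes the level: "All statistical tests will be two-sided and the statistical significance level will be set at 0.05 unless otherwise stated".

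The next paragraph of Section 7.1.2 treats the same kind of outcome differently. The frequencies of AF and of stroke or other focal neurologic events are to be "modeled with Poisson regression with the length of follow-up time as the offset".

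On observation time, Section 2.1 covers operations "in Massachusetts between 1/1/2012 and 12/31/2016", "with a follow-up period that extends to 12/31/2017". On death, Section 7.1.1 says: "For time-to-event data analyses, death will be considered a censoring event". That rule is confined to time-to-event analyses, and nothing equivalent is given for the comparison of mean counts. Section 1.2 reports that "preoperative AF is associated with a higher incidence of in-hospital postoperative AF, stroke, other cardiac morbidity and mortality", but gives no rate.

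**The concern.** A patient's raw event count is roughly the event rate multiplied by the time observed. A difference in mean counts therefore mixes a difference in rates with a difference in follow-up. If one group dies sooner, its mean count falls even when its event rate is the same.

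Two errors can follow. Groups with equal rates may be declared different. Or a true excess in the higher-mortality group may be reduced or erased. The second matters here because preoperative AF is the main risk factor in both primary aims, and by the plan's own background it is the group expected to die sooner. The plan would also hold two tests of event frequency, one adjusted for follow-up and one not, without saying which governs if they disagree.

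**Working it through.** **Inputs from the plan.** Surgery runs from 1/1/2012 to 12/31/2016 and follow-up ends on 12/31/2017 (Section 2.1). Potential follow-up from surgery is therefore 365 to 2,191 days, about 1 to 6 years. Section 4 gives 50,000 patients, of whom 4,000 have prior AF, so 46,000 do not; two-sided level 0.05.

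**The plan's own figure.** The plan states no figure for the mean-count comparison. The effect size in Section 4, which uses the same group sizes, reproduces: (1.960 + 0.842) × √(1/4,000 + 1/46,000) = 2.802 × 0.01648 = 0.0462, against 0.046 stated. From 25%, an effect of 0.046 leads to 27.0%, the stated 2-point difference.

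**Assumptions not in the documents.** Administrative censoring is uniform on 1 to 6 years in both groups. Death is exponential with rate d per year. The event rate r is equal in both groups, from 0.01 to 0.3 per year. Between-patient frailty variance θ is 0 or 2. The comparison is prior AF against none.

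**Formulas.** For time observed T, with C the administrative limit:

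- E[T] is the average over C of (1 − e^(−dC))/d.
- E[T²] is the average over C of 2(1 − e^(−dC)(1 + dC))/d².
- Mean count = r·E[T].
- Variance of a count = r·E[T] + r²·Var(T) + θ·r²·E[T²].
- z = |difference in mean counts| / √(V₁/4,000 + V₀/46,000).
- Rejection rate = Φ(z − 1.96) + Φ(−z − 1.96).

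**One case in full** (r = 0.10, death 0.08 v 0.04, θ = 0). Mean follow-up is 2.990 v 3.230 years, so mean counts are 0.2990 v 0.3230, a difference of 0.0240. Var(T) is 2.391 v 2.293, so V₁ = 0.2990 + 0.0239 = 0.3229 and V₀ = 0.3230 + 0.0229 = 0.3459. The standard error is √(0.3229/4,000 + 0.3459/46,000) = 0.00939. Then z = 2.56 and the rejection rate is 73%, with no difference in event rate.

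**Rejection rate under equal event rates** (where two values appear, θ = 2 gives the lower and θ = 0 the higher):

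| Death per year | Mean follow-up (years) | r = 0.01 | r = 0.02 | r = 0.10 | r = 0.30 |
|---|---|---|---|---|---|
| 0.04 v 0.04 | 3.23 v 3.23 | 5% | 5% | 5% | 5% |
| 0.05 v 0.04 | 3.17 v 3.23 | 5.5% | 6% | 8–10% | 10–19% |
| 0.06 v 0.04 | 3.11 v 3.23 | 7% | 9% | 17–25% | 24–56% |
| 0.08 v 0.04 | 2.99 v 3.23 | 13% | 20–22% | 50–73% | 69–99% |
| 0.08 v 0.03 | 2.99 v 3.29 | 18–19% | 29–32% | 70–90% | 87–100% |
| 0.10 v 0.04 | 2.88 v 3.23 | 22–24% | 37–42% | 83–97% | 95–100% |

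The first row shows that the 1-to-6-year spread alone leaves the test at its nominal level.

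**Simulation check** (1,000 replicates, θ = 0, r = 0.02, 0.10 and 0.25, death 0.04, 0.06 or 0.08 v 0.04). A Welch t test of mean counts agreed with the formula, for example 72.8% in the worked case. A rate test using person-time, equivalent to a two-group Poisson model with an offset, rejected in 4.3–6.3% of replicates across all nine scenarios.

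**Masking.** The ratio of mean counts under equal rates is the ratio of mean follow-up: 0.9075 for death 0.08 v 0.03 and 0.8915 for 0.10 v 0.04. A true excess of up to 1/0.9075 − 1 = 10% or 1/0.8915 − 1 = 12% would disappear from the raw means.

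**Overdispersion in the offset model.** With θ = 2 and r = 0.10, true variance exceeds Poisson variance by a factor of about 1 + θ·r·E[T²]/E[T] = 1 + 0.2 × 12.73/3.23 = 1.79. A nominal 1.96 threshold then behaves like 1.96/√1.79 = 1.47, which is a size of about 14%. The offset removes the follow-up bias, but recurrent events also call for robust standard errors.

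**The case against.** A reader might infer that 1 to 6 years of follow-up, cut by death, is enough to make groups with equal rates differ significantly. It is not: with the same follow-up distribution in both groups, rejection stays at 5%. A reader might also infer that surgery dates differ between the groups. Nothing in the documents says so. The only support for unequal follow-up is the link between preoperative AF and mortality in Section 1.2, which carries no rate.

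The case for leaving the text alone is fair in several respects:

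- The analysis that handles follow-up is already planned in the same section, and the primary aims use time-to-event and recurrent-event models.
- The AF and stroke shell tables in Section 12 (Tables 3 and 4) are labelled as time-adjusted, and no shell table is set aside for mean counts. That the paper would print two contradictory results is therefore conjecture.
- The disputed sentence names neither groups nor test, so the p-value might be meant to come from the Poisson model. The text neither says nor excludes this.
- For rare events and small mortality gaps the inflation is slight: 5.5–9% at 0.01–0.02 events per year with death 0.05–0.06 v 0.04.
- Prior-AF patients may well have the higher event rate, so a weakened excess is more likely than a falsely protective result.

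All of this limits the importance of the point. It does not remove it: as written, the section commits to a significance test of raw means that needs equal mean follow-up to be valid, in a setting where the plan gives a reason to doubt that.

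**Conclusion.** The point holds in a limited form. The test of mean counts is unreliable as a test of event rates whenever mean follow-up differs between the compared groups. The size depends almost wholly on quantities the documents do not give: from 5%, with equal mortality, to nearly 100%, with mortality about 2.5 times higher and frequent events. Moderate gaps (0.06 v 0.04 per year) give 7–56%. These figures assume the prior-AF split of Section 4, uniform censoring and exponential death.

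The consequence is confined to a redundant p-value for a secondary aim. No primary aim depends on it, and the documents do not show that any published conclusion would be reversed.

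**What to change.** In Section 7.1.2, delete the p-value for the difference in mean counts. Name the groups to be compared. For each count outcome, report events per 100 person-years by group, with a rate ratio, 95% confidence interval and two-sided p-value from the planned Poisson model with follow-up time as offset. Use standard errors robust to overdispersion, because events recur within patients. Mean and standard deviation of counts may stay as description only, preferably beside mean follow-up by group.

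The cost is SAP wording only. The events and follow-up times are already needed for the planned model, so no new data are required.

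### The secondary Poisson models use one follow-up offset, so if AF is concentrated early, the average rates and the rate ratios for covariates tied to follow-up length depend on how long patients were followed

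*Combined protocol and SAP*

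**What the plan says.** Section 7.1.2 of the combined protocol and SAP states that the frequencies of AF and of stroke or other focal neurologic events "will be modeled with Poisson regression with the length of follow-up time as the offset". It names no time-since-discharge term, no division of person-time and no check that the rate is constant. These models serve Secondary Aims 1 and 2 (Section 2.4).

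Section 2.1 places surgery "between 1/1/2012 and 12/31/2016, with a follow-up period that extends to 12/31/2017".

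Section 1.2 bears on the timing of AF in three places:
- It describes the usual view: "Conventional management of postoperative AF assumes that it results from self-limited causes".
- It cites a continuous-monitoring study in which the incidence of at least one episode was "60% over the entire follow-up period and 39% occurring more than 3-months after surgery".
- It links prior AF to survival: "preoperative AF is associated with a higher incidence of in-hospital postoperative AF, stroke, other cardiac morbidity and mortality".

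The Table 1 shell in Section 12 tabulates post-discharge AF and stroke in windows that are narrow at first (30, 90, 182 and 365 days) and yearly after that, up to 5 years. Section 7.1.1 uses Cox, Andersen-Gill (AG) and Prentice-Williams-Peterson (PWP) models for the primary aims.

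**The concern.** A Poisson model with total follow-up as its only time element estimates events divided by person-time. That is a sufficient summary only if the rate does not change over follow-up. If the rate is high early and lower later, a patient followed for 18 months has a higher average rate than one followed for 66 months, even when their risk is identical at every time point.

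Follow-up differs about fourfold between the first and last surgery years because accrual lasts five years and there is one closing date. Death adds further differences. Two outputs are exposed: the average rate reported as the frequency, and the rate ratio for any covariate associated with follow-up length. Year of operation is a listed characteristic in Table 1. Prior AF, the main risk factor, is linked to follow-up length through mortality.

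**Working it through.** **The plan's own figure.** The only design calculation (Section 4) concerns a difference in proportions, not this model. It reproduces: h = (1.960 + 0.842) × √(1/4,000 + 1/46,000) = 0.0462, and h = 0.046 from 25% gives 27.0%. The plan gives no figure for the Poisson model, so what follows rests on stated assumptions.

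**Step 1. Follow-up, from the dates in Section 2.1.** Surgery in 2016 gives 1-2 years to 12/31/2017; surgery in 2012 gives 5-6 years. Across the cohort the range is about 1-6 years, counted from surgery and before death.

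**Step 2. How front-loaded might AF be?** The documents give no post-discharge rate by time. The 60% and 39% in Section 1.2 are read as percentages of patients with an episode.
- Early episode probability a: at least 60% − 39% = 21%. If early and late episodes are independent, a = 1 − 0.40/0.61 = 34%.
- Length F of the cited study is not given; assume 1 to 3 years.
- Early hazard = −ln(1 − a)/0.25. Late hazard = −ln(0.61)/(F − 0.25).
- Lowest: a = 0.21, F = 1: 0.943/0.659 = 1.4.
- Highest: a = 0.344, F = 3: 1.688/0.180 = 9.4.

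The early/late ratio k is therefore taken as 1.4 to 9.

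**Step 3. Formula.** Let the rate be k times higher in the first 0.25 year than afterwards, and identical in both groups compared (true ratio 1). With yearly death rate m (exponential) and administrative follow-up uniform on (a₁, b₁):
- early person-time E = (1 − e^(−0.25m))/m
- total person-time T = 1/m − (e^(−m·a₁) − e^(−m·b₁))/(m²(b₁ − a₁))
- average rate relative to the late rate, R = 1 + (k − 1)E/T
- apparent rate ratio = R₁/R₀

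**Step 4. Surgery in 2016 v 2012, m = 4% in both.** E = 0.2488; T = 1.454 and 4.936 years.

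| k | R, 2016 | R, 2012 | Apparent ratio |
|---|---|---|---|
| 1 | 1.000 | 1.000 | 1.00 |
| 1.4 | 1.068 | 1.020 | 1.05 |
| 9 | 2.368 | 1.403 | 1.69 |

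The two R columns also show the problem for the reported frequency. At k = 9 the average rate is 2.37 times the late rate in one surgery year and 1.40 times in the other, with the same underlying risk.

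**Step 5. Prior AF through mortality, follow-up 1-6 years.** Section 1.2 gives a direction but no death rates, so these are assumed.

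| Yearly mortality, prior AF v none | T (years) | k = 1.4 | k = 9 |
|---|---|---|---|
| 8% v 4% | 2.990 v 3.230 | 1.002 | 1.029 |
| 10% v 4% | 2.880 v 3.230 | 1.003 | 1.043 |
| 15% v 5% | 2.630 v 3.167 | 1.006 | 1.073 |

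**Step 6. Balanced follow-up.** If both groups have the same follow-up distribution, E/T is the same and R₁/R₀ = 1 for every k.

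**The case against.** The strongest reply is that Secondary Aims 1 and 2 ask for frequency, while risk-factor effects belong to the primary aims. Those use Cox, AG and PWP models, which leave the baseline rate free, and AG already addresses overall recurrent-event intensity. Counts by window and time-course figures are also planned. This stands as a limit on scope. It does not repair the secondary models, because the plan does not state person-time rates by window and the Poisson model still reports averages that depend on the follow-up mix.

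Second, the evidence for an early peak is indirect. Section 1.2 presents self-limited causes as an assumption of conventional management and then qualifies it. The 60% and 39% come from continuous monitoring, count from surgery rather than discharge, and, by the title in the reference list, concern new-onset postoperative AF. The Table 1 windows are descriptive. All of this stands: front-loading is a reasonable inference, not a documented fact.

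Third, the larger distortion concerns surgery year, which is not a declared exposure, and it is the most extreme contrast. If year of operation enters the model it absorbs the calendar component for other covariates, but Section 7.1.2 does not require it. Including it would not remove the mortality component or correct the year coefficient itself.

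A reader might infer more than the documents support:
- **That all rate ratios are biased.** Step 6 shows that they are not.
- **That the surgery-year ratio could roughly double.** A value of 1.99 needs an early/late ratio of 15, which the documents give no basis for choosing.
- **That stroke is equally affected.** The documents give no timing for stroke.
- **That items recorded in only one STS version are distorted.** The documents do not date the versions, and Section 7.3 drops covariates with more than 33% missing.
- **That the distortion for prior AF matches the effect the study is sized for.** 27%/25% = 1.08 is a ratio of proportions and not comparable with a Poisson rate ratio.

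**Conclusion.** The concern holds in a limited form. The single offset assumes a constant rate, the plan does not address this, and follow-up is very unequal by design. If AF is front-loaded by a factor of 1.4 to 9 over the first 3 months, the reported average rate depends on the follow-up mix. A true rate ratio of 1 then appears as about 1.05-1.69 for 2016 v 2012 surgery, and about 1.00-1.07 for prior AF through mortality.

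The factor k, the death rates, uniform entry and exponential death are assumptions. The 34% behind the upper k assumes independence and is not a strict bound; positive dependence between early and late episodes would raise it. With a constant rate or balanced follow-up there is no distortion. The primary analyses are unaffected, and no size is shown for stroke. For the main risk factor the effect is small, so this is an inexpensive improvement to a secondary analysis and does not threaten the study's main conclusions.

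**What to change.** In Section 7.1.2, divide each patient's post-discharge follow-up at the Table 1 cut points (30, 90, 182 and 365 days, then yearly). Table 1 stops at 5 years and follow-up can approach 6, so continue the yearly windows to the end of follow-up. Fit the Poisson model with window as a factor and the log of person-time in the window as the offset; writing log also settles the offset's scale. Report the event rate in each window as the frequency, and window-adjusted rate ratios for the risk factors. This removes the distortion, apart from any change in rate within a window.

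The cost is one extra data step, a few lines of SAP text and somewhat more reporting. No new data are needed.

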7.2 Pooling of Sites

The data will be pooled across all participating sites. In logistic and Cox proportional hazards models, site will be treated as a random effect.

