7.4.3 Examination of Subgroups

To determine if all subgroups experience similar treatment effects or if there are subgroups that behaved differently. We will report odds ratios with 99% confidence intervals for the primary outcome by the following subgroups, with/without prior atrial fibrillation before surgery, and with/without atrial fibrillation when discharged. We will conduct a test of homogeneity of effects across the subgroups and report a P value. Unless there is strong evidence against the null hypothesis of homogeneity of effects (i.e. $p<0.001$) the overall odds ratios will be considered as the most reliable guide to the approximate relative risks in all subgroups.

7.4.4 Correlated data, bias, confounding and interactions.

Collinearity between risk factors will be evaluated with Variance Inflation Factors (VIF) or generalized VIF. Risk factors with high VIF (>2.5) will be excluded in the models.

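### The Poisson model for event frequencies makes no allowance for repeated events in the same patient, so AF rate-ratio intervals in this secondary analysis could be too narrow

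*Combined protocol and SAP*

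**What the plan says.** Section 7.1.2 (Secondary Aims) names the outcomes, "The frequencies of atrial fibrillation and stroke or other focal neurologic event", and says that they "will be modeled with Poisson regression with the length of follow-up time as the offset". It adds that covariates will be chosen from univariate tests and clinical judgement. It says nothing on how the variance is estimated.

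The plan expects more than one event per patient. Section 7.1.1 opens its recurrent-event paragraph with "Since there might be repeated occurrences of atrial fibrillation and stroke or other focal neurologic event for each patient" and continues "we will use the Andersen-Gill (AG) model and the Prentice, Williams and Peterson (PWP) models to analyze recurrent events data". No variance estimator is named for those models either.

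Three other places might have filled the gap, and none does:

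- Section 7.2 has a random effect, but for site and not for patient, and the Poisson model is not listed: "In logistic and Cox proportional hazards models, site will be treated as a random effect".
- Section 7.4.4 has correlated data in its title, but deals only with correlation between risk factors: "Collinearity between risk factors will be evaluated with Variance Inflation Factors (VIF) or generalized VIF".
- Section 7.6 compares the Andersen-Gill (AG) and Prentice-Williams-Peterson (PWP) results for consistency, which does not correct a standard error.

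**The concern.** A Poisson model sets the variance of each count equal to its mean, given the covariates. If some patients have a persistently higher rate of AF than their measured covariates explain, the variance of the counts exceeds the mean. The model-based standard error is then too small, the confidence interval too narrow and the p-value too low.

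What is at stake is the error rate the plan sets itself. Section 4 states "All statistical tests will be two-sided and the statistical significance level will be set at 0.05 unless otherwise stated", and section 7.4.2 makes no multiplicity adjustment, so nothing downstream offsets an inflated test. If the univariate screening in section 7.1.2 uses the same Poisson model, understated p-values would also affect which risk factors enter the final model.

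**Working it through.** **The plan's own figure.** Section 4 has the only design calculation. It assumes "Assuming 50,000 patients will be included in the analysis, among which 4000 (8%) have prior AF". The detectable Cohen's effect size at 80% power is (1.960 + 0.842) × √(1/4,000 + 1/46,000) = 0.0462, against 0.046 stated. From 25%, h = 0.046 gives 27.02%, a difference of 2.02 points against 2% stated. The figure reproduces. It concerns a comparison of two proportions and says nothing about the Poisson model.

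**Inputs.**

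- Two-sided 5% test (section 4).
- Surgery from 1/1/2012 to 12/31/2016, followed to 12/31/2017 (section 2.1), so about 1 to 6 years per patient. *Assumed* uniform, with no shortening by death.
- *Assumed* AF rate r = 0.1 events per patient-year. As a rough anchor, if the 25% in section 4 were the share with at least one post-discharge AF event over a mean of 3.5 years, a common rate would be −ln(0.75)/3.5 = 0.082 per year. The plan does not say that the 25% means this.
- *Assumed* stroke rate of 0.01 to 0.02 per patient-year; the documents give none.
- *Assumed* gamma frailty (a patient-specific multiplier of the rate) with mean 1 and variance v from 0.5 to 5.
- No true group effect and no covariates.

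**Formula.** For follow-up t, a count has mean rt and variance rt + v r² t². Summed over patients, the ratio of the true to the model-based variance of the log rate is

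φ = 1 + v · r · E[t²]/E[t].

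It is the same in both groups, so it does not depend on the sample size or the 8%/92% split. With t uniform on 1 to 6, E[t] = 3.5, E[t²] = (6³ − 1³)/(3 × 5) = 14.33, and the ratio is 4.095. The Poisson standard error is 1/√φ of the true one, and the actual type I error is 2 × [1 − Φ(1.96/√φ)].

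| Assumed rate per year | v | φ | Poisson SE / true SE | Type I error |
|---|---|---|---|---|
| 0.1 (AF) | 0.5 | 1 + 0.5 × 0.1 × 4.095 = 1.205 | 0.91 | 7.4% |
| 0.1 | 1 | 1.410 | 0.84 | 9.9% |
| 0.1 | 2 | 1.819 | 0.74 | 14.6% |
| 0.1 | 5 | 3.048 | 0.57 | 26.2% |
| 0.02 (stroke) | 2 | 1.164 | 0.93 | 6.9% |
| 0.02 | 5 | 1.410 | 0.84 | 9.9% |
| 0.01 (stroke) | 1 | 1.041 | 0.98 | 5.5% |
| 0.01 | 2 | 1.082 | 0.96 | 6.0% |
| 0.01 | 5 | 1.205 | 0.91 | 7.4% |

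**Checks by simulation.**

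- 50,000 patients, 8% exposed, 1,000 replicates, v = 2 and 5: plain Poisson rejected in 14.6% and 25.2% at 0.1 per year, and in 6.0% and 11.4% at 0.02 per year. The Monte Carlo standard error near 10% is √(0.1 × 0.9/1,000), about 1 percentage point. Patient-level robust variance gave 3.6% to 6.1%.
- 5,000 patients, 4,000 replicates, v = 1, 2 and 5: at 0.082 per year plain Poisson rejected in 9.7%, 12.4% and 21.3%; at 0.01 per year, in 5.0%, 6.2% and 6.9%. Robust variance gave 4.7% to 6.3% over all settings run, including v = 0 and v = 10.

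The AG and PWP models were not simulated.

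**The case against.** The strongest reply is that the plan is silent on the variance and has not chosen a bad one. An analyst could report sandwich standard errors and still comply with section 7.1.2. That stands, so the finding is conditional on model-based variance. But section 1 presents this document as the one that codifies the analysis, and a reader who follows it literally would fit an ordinary Poisson model.

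It is also fair to say that the size is not in the documents. Section 7.1.1 says only that events might recur and gives no recurrence distribution. The calculation has no covariates, whereas the planned model has selected risk factors; only the heterogeneity they leave unexplained inflates the final test. Deaths would shorten follow-up and lower φ. Section 7.1.2 also promises means and standard deviations for count outcomes, so marked over-dispersion would be visible, although no rule says what to do about it.

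A reader might infer four stronger things that the documents do not support:

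- *That stroke tests run far above 5%.* At plausible low rates the inflation is small, because few patients have a second event.
- *That the main analyses are compromised.* The Poisson model serves secondary aims on frequency. The risk-factor questions in section 2.3 are answered first by Cox models of time to first event, which over-dispersion of counts does not touch.
- *That the rate ratios are biased.* Over-dispersion in itself affects their precision, not their value.
- *That the AG and PWP results would be wrong.* The plan does not name their variance estimator and the effect was not quantified, so only a request for clarification is justified.

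**Conclusion.** The concern holds in a limited form. The plan expects repeated events, models their frequency by Poisson regression, and nowhere allows for variation between patients beyond the covariates. If the model-based variance is used, AF rate-ratio intervals in this secondary analysis are too narrow whenever such variation exists.

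The direction is firm; the size is illustrative. Type I error is about 7% to 26% for AF at an assumed 0.1 events per year, frailty variance 0.5 to 5, follow-up of 1 to 6 years and no covariates, and about 5% to 10% for stroke at an assumed 0.01 to 0.02 events per year. This should be corrected, but it does not threaten the time-to-first-event results.

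**What to change.** In section 7.1.2, replace the sentence on Poisson regression with:

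> Event counts will be modelled by Poisson regression with patient-level robust (sandwich) variance and log follow-up time as offset; negative binomial regression will be a sensitivity analysis and the dispersion statistic will be reported.

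Naming one primary method keeps the choice from being made after the data are seen.

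For consistency, add to section 7.1.1, as a clarification:

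> The Andersen-Gill and PWP models will use robust variance clustered on patient.

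The patient-level correction does not deal with clustering by site. Section 7.2 should therefore also say how site enters the Poisson model, which it does not currently list.

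The cost is one or two sentences, plus a phrase on site. No new data are needed. Some intervals become wider, and if the counts prove not to be over-dispersed the results barely change.
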